The randomized intervention kit number list is generated centrally by BMS and IMPs are packaged in accordance with this list. The randomization and intervention allocation are performed centrally by the Early RA 3TR Database, which generates the participant randomization list and allocates the intervention number and the corresponding intervention kits to the participants according to it.

A randomized participant is defined as a participant who has been allocated to a randomized intervention regardless of whether the intervention kit was used or not (ie, participants registered by the Early RA 3TR Database in the 3TR-PARTNER-RA study). A participant cannot be randomized more than once in the study.

The result (i.e. randomised treatment arm) will then be filled to the local site staff (each site will have a nominated joint assessor). The local site staff will immediately be able to see the result of the randomisation, however, they will be blinded to any information about the patient's biopsy result.

Randomisation methods and procedures will be described within the Database User Manuals and Data Management Plan.

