# 7.4 Blinding

Neither the participant nor any of the investigators or site staff who are involved in the treatment or clinical evaluation and monitoring of the participants will be aware of the study intervention received.

- The study drug and placebo will be provided in blinded treatment kit numbers obtained through the Early RA 3TR Database. Abatacept 125 mg and placebo matching will be provided in identically matched prefilled syringes that are visually indistinguishable. Syringes and boxes will be labelled with a kit number.
- Unblinded personnel will include designated representative(s) from the Sponsor or QMUL-designed personnel to review unblinded data.
- Blinded personnel will include designated representative(s) from the study site, and Sponsor. Administration of the study drug will be completed by blinded study site personnel. The study drug will be administered in the same manner to maintain the blindness of the treatment allocation.

The randomization code should not be broken except in medical emergencies when the appropriate management of the participant requires knowledge of the treatment randomization. The investigator documents and reports the action to the Sponsor, without revealing the treatment given to the participant to the Sponsor staff.

The Sponsor retains the right to break the code for SAEs that are unexpected and are suspected to be causally related to an investigational medicinal product and that potentially require expedited reporting to regulatory authorities. Randomization codes will not be broken for the planned analyses of data until all decisions on the evaluability of the data from each individual participant have been made and documented.

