#### 7.5.4 Follow-up (visits 4-7)

Patients will be monitored on a 4-weekly basis as shown in the study visit schedule (Table 1), Section 8.2). Patients will be followed up to 16 weeks. If the study is running at the particular site, there is a potential for patients to be recruited into a long term follow up study: CReMSIA (REC ref: 17/EE/0119). Data collection in the CReMSIA study will be recorded in an electronic CRF. Patients will be followed up as per best practice as currently done in the academic centre participating in the trial.

Safety blood tests will be undertaken every 4 weeks. Additional blood tests for monitoring of toxicity/safety of therapy may be undertaken at the physician's discretion. The ACR 50, a validated composite end point, will be used to assess response to therapy as the primary outcome measure. The Health Assessment Questionnaire, EQ-5D-5L and SF-36 will be used to gauge functional ability and improvement in other aspects of the patients' life. The ESS will be used to measure a patient's sleepiness.

Visits 4 - 7 will be carried out every 4 weeks (±7 days) from the baseline visit. The Principal Investigator will need to review any non-compliance with a view to withdrawing patients at their discretion if drug schedule is adversely affected. Patients who consent to the biopsy procedure at Visit 7 (Week 16) will be asked to complete the Pre Biopsy Assessment Form at Visit 7 (week 16) and the Post Biopsy Assessment Form at the safety follow up visit. If the safety

follow-up visit is completed over the phone, this questionnaire will be completed over the phone.

As per normal clinical practice, the GPs of participants with active RA and a cardiovascular risk profile will be informed and asked to review treatment.

All joint assessments from baseline will be performed by a member of the local trial team who will be blinded to treatment allocation. The joint assessor should also complete the VAS physician assessment component of the VAS Pain Score questionnaire. Data will be entered in the electronic CRF by the Investigator or designee who will also coordinate data validation checks and query resolution.

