Participants will not have access to the study intervention after the end of their participation and may return to the standard of care received prior to entering the study, at the discretion of their physician. At the end of week 16, the treatment allocation will be unblinded to allow the physician and the participant to decide the standard of care. This will generate an email sent also to the QMUL clinical trial team. The principal investigator will report the treatment allocation on the e-CRF.

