#### 12.6.2 Procedures for reporting blinded SUSARs

The CI, as sponsor medical assessor, will assess the event blinded for all possible IMPs, placebos, and combinations.

The Joint Research Management Officer (JRMO) at Queen Mary University of London will be unblinded to facilitate unblind SUSAR reporting to the MHRA. A delegated and trained JRMO will have access by an account with limited access to the Early RA 3TR Database to unblind the participants independently. The IT Systems and Project Manager will report the IMP to Joint Research Management Officer to enable them to report to MHRA in case of issues in accessing the Database from the delegated JRMO.

A delegated member from the clinical team will be responsible for maintaining unblinded records for the trial. This will be recorded in the delegation log for the study.

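### Section 7.3 gives site staff the randomised arm at once, which contradicts the blinding rules in 7.4 and 7.4.1; the order of week-16 unblinding and visit 7 assessment is also left open

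*Protocol*

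**What the plan says.** **Release of the arm.** Protocol section 7.3 states: "The result (i.e. randomised treatment arm) will then be filled to the local site staff". The same sentence notes that each site has a nominated joint assessor. The next one adds: "The local site staff will immediately be able to see the result of the randomisation". The only item held back is the biopsy finding: "they will be blinded to any information about the patient's biopsy result". Earlier in 7.3, local site staff are identified as the principal investigator or research nurse.

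**The blind.** Section 7.4 covers "Neither the participant nor any of the investigators or site staff who are involved in the treatment or clinical evaluation and monitoring" of participants; none of them is to know the intervention. It provides for coded kits, matched syringes and administration by blinded site personnel. It limits code breaks to medical emergencies, apart from the sponsor's right for certain serious events. Section 7.4.1 lets the investigator reveal an allocation only through a request with a reason and a password.

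**Planned unblinding.** Section 7.7 states: "At the end of week 16, the treatment allocation will be unblinded to allow the physician and the participant to decide" the standard of care. Elsewhere the same section places unblinding at the end of the trial. On timing, section 7.5.4 says: "Visits 4 - 7 will be carried out every 4 weeks (±7 days) from the baseline visit". The week-16 unblinding triggers an e-mail that also goes to the sponsor university's clinical trial team, and the principal investigator enters the arm in the eCRF.

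**Event assessment.** Under 12.6.2 the chief investigator "will assess the event blinded for all possible IMPs, placebos, and combinations". Section 12.4 continues adverse event reporting for at least 30 days after the week-16 visit.

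**The concern.** Sections 7.3 and 7.4 give the same people opposite instructions. Because 7.3 itself explains the result as the treatment arm, it cannot be read as meaning only a kit number. It also says that the procedures will be carried into the database user manuals and data management plan, so the sentence could be built into the system.

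If it were, the staff who treat patients would know the arm. They have discretion over corticosteroids (11.15.3) and over stopping treatment or withdrawing a participant (8.1). The joint assessor is to be blinded but comes from the same local team (7.5.4). Every CDAI component is a joint count or a global rating (7.6.4), with no laboratory item to anchor it.

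The order at week 16 matters for a related reason. Under 7.7 only placebo patients may move to the follow-on trial, and only if disease activity is moderate or high. Knowing the arm before visit 7 is scored would create an incentive confined to one arm.

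**Working it through.** This is mainly a comparison of text. The arithmetic only delimits the consequence.

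1. **Can 7.3 and 7.4 both be followed?** Section 7.3 gives the arm to the principal investigator or research nurse, immediately. Section 7.4, speaking of the intervention, denies that "any of the investigators or site staff who are involved in the treatment or clinical evaluation and monitoring of the participants will be aware"; its sentence opens with a negative. The staff groups overlap, so the two cannot both be met. The code-break steps in 7.4.1 would also serve no purpose for someone who already sees the arm.

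2. **When would disclosure occur?** The schedule in 7.2 puts randomisation at visit 2 and baseline CDAI at visit 3. Both the baseline and the week-16 score would be collected after the arm was shown.

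3. **Who scores the CDAI?** From 7.6.4: 28 tender + 28 swollen + 10 patient global + 10 physician global = 76. The blinded joint assessor supplies 28 + 28 + 10 = 66 (7.6.3, 7.6.5). The patient supplies the other 10, and 7.3 does not send the arm to patients.

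4. **Which contrasts are exposed?** Suppose knowledge of the arm shifts mean CDAI change by b_A on abatacept (Groups 1 and 3) and by b_P on placebo (Groups 2 and 4), whatever the biomarker status.
   - Primary, 1 − 3: b_A − b_A = 0.
   - Biomarker by treatment, (1 − 2) − (3 − 4): (b_A − b_P) − (b_A − b_P) = 0.
   - Simple abatacept − placebo, 1 − 2 or 3 − 4: b_A − b_P, which does not cancel.

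   If the shifts differ by biomarker status (+ or −), the primary contrast moves by b_A+ − b_A−, and the interaction by (b_A+ − b_P+) − (b_A− − b_P−).

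5. **Visit 7 window.** 16 × 7 = day 112, and ±7 days gives days 105 to 119. If the end of week 16 means day 112, a visit on days 113 to 119 is in window but after the stated unblinding point.

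6. **Sample size.** Section 14.1 is unaffected. With a two-sided 5% level (assumed; 14.1 does not state it), n per group = 2 × 14.34² × (1.960 + 1.282)² / 10² = 43.2, rounded up to 44. Then 4 × 44 = 176, and 176 / (0.95 × 0.95) = 195.01, rounded up to 196, as the protocol states.

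**The case against.** The strongest reply is that one sentence conflicts with an otherwise coherent blinded design: a randomisation list closed to end users, coded kits, matched syringes, blinded administration and a controlled code break. That stands. A reader might infer that the trial is unblinded by design. The protocol does not support this; it shows a contradiction whose effect depends on which sentence is carried out.

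A reader might also infer that the primary result is biased, or express an abatacept-placebo scoring error as a share of the 10-point planning difference. Neither follows. The 10 points are the difference between Groups 1 and 3, both on abatacept, so that ratio would compare unlike contrasts. Sites do not see the biopsy result, and a uniform error cancels as shown. The blinded assessor is a real safeguard, weakened only by belonging to the team that 7.3 would inform.

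On week 16, the protocol also uses that term as the label for visit 7, and 7.7 deals with care after the trial. The natural reading is that assessment comes first. The text does not instruct early unblinding; it omits the order.

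On event assessment, the planned e-mail goes to the clinical trial team. The chief investigator is named as a recipient only for emergency code breaks (7.4.1). Some unblinded sponsor roles are foreseen in 7.4 and 12.6.2. This supports reconciling the recipients, not a claim that blinded assessment has failed.

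**Conclusion.** The contradiction between 7.3 and 7.4/7.4.1 is established from the text and applies to every randomised participant. If 7.3 is carried out as written, the blind is lost for treating staff and at risk for the joint assessor. The exposed results are mainly simple abatacept-placebo comparisons and safety, together with discretionary steroid and withdrawal decisions.

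No bias is demonstrated in Group 1 versus Group 3. The biomarker-by-treatment contrast is biased only if the error differs by biomarker status, which the documents do not show. The cancellation is exact for mean CDAI change under a uniform shift and only approximate for responder endpoints. The documents give no basis for a size of bias in CDAI points, so none is offered.

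The week-16 matter is a missing ordering rule, with up to 7 days in which the wrong order is possible. The planned unblinding also falls outside the code-break exceptions in 7.4. No sample size or power figure changes.

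**What to change.** - **7.3:** replace the sentences on disclosure so that site staff receive only the randomisation number and kit number, never the arm. Make the database manual match, and check what the trial database actually displays to site accounts.
- **7.7:** state once that planned unblinding of a participant takes place only after that participant's visit 7 joint counts, global scores and questionnaires are completed and recorded. Align the two descriptions of the trigger. A full CRF lock is not needed. Section 15.2 gives sites about a week to complete CRFs, and waiting for a lock could delay the care decision that the unblinding serves.
- **7.4:** list the planned week-16 unblinding as an exception to the emergencies-only rule.
- **7.4, 7.4.1, 7.7 and 12.6.2:** reconcile who receives unblinding e-mails with who must assess events blinded. For emergency code breaks, 7.4 keeps the treatment from sponsor staff, while 7.4.1 e-mails the chief investigator and the sponsor university's clinical team.

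The cost is protocol and manual wording and possibly a change of database permissions. It needs no extra patients or visits. Emergency unblinding and disclosure to physician and participant after visit 7 are both kept.

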# 7.4 Blinding

Neither the participant nor any of the investigators or site staff who are involved in the treatment or clinical evaluation and monitoring of the participants will be aware of the study intervention received.

- The study drug and placebo will be provided in blinded treatment kit numbers obtained through the Early RA 3TR Database. Abatacept 125 mg and placebo matching will be provided in identically matched prefilled syringes that are visually indistinguishable. Syringes and boxes will be labelled with a kit number.
- Unblinded personnel will include designated representative(s) from the Sponsor or QMUL-designed personnel to review unblinded data.
- Blinded personnel will include designated representative(s) from the study site, and Sponsor. Administration of the study drug will be completed by blinded study site personnel. The study drug will be administered in the same manner to maintain the blindness of the treatment allocation.

The randomization code should not be broken except in medical emergencies when the appropriate management of the participant requires knowledge of the treatment randomization. The investigator documents and reports the action to the Sponsor, without revealing the treatment given to the participant to the Sponsor staff.

The Sponsor retains the right to break the code for SAEs that are unexpected and are suspected to be causally related to an investigational medicinal product and that potentially require expedited reporting to regulatory authorities. Randomization codes will not be broken for the planned analyses of data until all decisions on the evaluability of the data from each individual participant have been made and documented.

#### 7.4.1 Procedures for Unblinding

The Early RA 3TR Database for the 3TR-PARTNER-RA study will be programmed with blindbreaking instructions. In case of an emergency, the Investigator, as the doctor responsible for the treatment, has the sole responsibility for determining if unblinding of a participant's treatment assignment is warranted. Participant safety must always be the first consideration in making such a determination. If the Investigator decides that unblinding is warranted, the Investigator may, at the Investigator's discretion, contact the Sponsor to discuss the situation prior to unblinding a participant's treatment assignment unless this could delay emergency treatment for the participant. If a participant's treatment assignment is unblinded, the Sponsor must be notified within 24 hours of this occurrence. The date and reason that the blind was broken must be recorded in the source documentation and database (e-CRF), as applicable.

The code breaks for the study will be held in the Early RA 3TR database back-end with the Data Safe Heaven (ITS) as back-up and are the responsibility of EMR IT Systems and Project Manager. In the event a code break is required, the Investigator or responsible delegate will use the code break to confirm the participant's treatment allocation and relay this information to the required individuals. If the person requiring the unblinding is not associated with the study team, that health care professional will notify the Investigator team that an unblinding is required for a study participant.

In the Early RA 3TR database a 24/7 unblinded procedure will be in place with a code breaks page accessible only to the Investigator or responsible delegate such as the Co-investigator. To unblind the participant:

- 1. Investigator or responsible delegate will be required to access the database accessible 24/7
- 2. Open the patient page and click on the "Unblind" tab
- 3. Request to unblind the patient, add the reason and their password to verify their request.
- 4. The Early RA 3TR database will unblind the treatment allocation and show it on the patient record.
- 5. An automatic email will be generated by the Database and sent to the local site contacts and the Chief Investigator and clinical team at QMUL.

The PI or delegate will notify the CI in writing as soon as possible following the code break detailing the necessity of the code break.

In case of patient presents to A&E, the patient will be advised to bring with them the Patient Diary Card for the duration of the study. On the card will be reported the "Rheumatology Study Team Telephone" in case the patient needs to be unblinded for an emergency. Following the contact with the local Rheumatology Study Team, the PI or delegate will log in to the database, as detailed above, and unblind the patient as requested by the A&E doctors.

In case the patient does not have the card with them and therefore contacting the local Rheumatology Study Team will be impossible, they will be treated as if on active arm (Abatacept).

#### 7.5 Study assessments

All trial activities and the visits at which they should be undertaken are documented in the "Schedule of Assessments" table.

#### 7.5.1 Screening procedures (visit 1)

During the screening visit, written informed consent will be obtained from all patients by the Principal investigator or his/her designee before any protocol-specific procedure is performed. Study details, risks and benefits will all be reviewed and patients will be encouraged to ask questions and clarify any concerns. Demographic data (including age, assigned sex at birth and race) and medical history will be obtained. Patients, both men and women, will be reminded to use an acceptable and effective method of contraception during the study period and the appropriate time period after stopping study treatment. Patients may be screened up to 6 weeks prior to baseline visit. As per the study visit schedule screening will entail evaluation of:

- Inclusion and exclusion criteria
- Demographic data including age, assigned sex at birth, and race
- 2010 ACR/EULAR RA classification criteria
- Systemic disease assessment (RA involvement)
- Medical history
- Procedures history
- Allergies
- Concomitant medication
- DMARD therapy
- Corticosteroid therapy
- Clinical examination
- Rheumatoid Factor (RF) and Anti-CCP antibodies (CCP)a
- Routine blood tests (ESR, CRP, Full blood count (Haemoglobin, Red Cell Count,

- Haematocrit, White Blood Counts + differential including lymphocytes and
- neutrophils, Platelet count) liver function tests (ALT, AST), Kidney function/U&E (urea, sodium, potassium, creatinine, eGFR)b
- Total cholesterol, HDL, LDL, and triglycerides
- Hepatitis serology, HIV and IGRAc
- Vital signs
- Chest X-rayd
- ECG
- Pregnancy teste
- Joint assessment
- ACR-core set measures
- DAS 28 assessment
- Clinical Disease Activity Index (CDAI)
- VAS Pain score
- US assessmentf

Note: Anti-TNF therapy screening to include TB screening (IGRA), screening for Hepatitis and HIV according to local guidelines.

a RF/CCP tests should be performed unless these tests have been done previously and do not need repeating as per local guidelines.

b Routine blood tests do not need to be taken if the patient has already had these performed within 3 weeks of the screening visit

c Hepatitis B screening must be performed unless it has been done in the preceding 3 months of the screening visit. If core antibody result is positive but the surface antigen and the viral load result is negative it is assessed as indicating a 'negative' overall result and therefore result is deemed as negative. TB (IGRA), Hepatitis C, and HIV screening is not mandatory; however, all centres are expected to act according to local guidelines with respect to patient screening prior to Anti-TNF and sarilumab therapy.

dA chest x-ray must be performed as screening for tuberculosis prior to biological therapy. A chest x-ray must be done at the screening visit to confirm the patient's eligibility, unless a chest X-Ray has been done in the preceding 3 months of the screening visit and the patient must not have had any pulmonary symptoms since then.

eA pregnancy test will be performed at each study visit for female patients of childbearing age irrespective of the use of contraceptive methods.

fUS assessment will be of the joint selected for biopsy to ensure that there is sufficient thickening to meet the following inclusion criterion: selected joint for biopsy must be minimum grade 2 synovial thickening, as assessed at the biopsy visit. This scan will not be reviewed centrally and is optional and not required if the site is confident that the joint will show sufficient inflammation at the biopsy visit.

Note: examples of reliable forms of contraception during the trial are: oral contraceptive and condom, intra-uterine device (IUD) and condom, diaphragm with spermicide and condom. Patients should continue to use a reliable form of contraception for 3 months after their last treatment if on sarilumab, or 3 weeks after their last treatment if they are on etanercept. Males with a partner of childbearing potential, will also be asked to use contraception for the duration of the study.

Note: a woman is considered of childbearing potential (WOCBP) i.e. fertile, following menarche (first occurrence of menstruation) and until becoming post-menopausal unless permanently sterile. Permanent sterilisation methods include hysterectomy, bilateral salpingectomy and bilateral oophorectomy.

Note: a postmenopausal state is defined as no menstruation for 12 months without an alternative medical cause. A high follicle stimulating hormone (FSH) level in the postmenopausal range may be used to confirm a postmenopausal state in women not using hormonal contraception or hormonal replacement therapy. However, a single FSH measurement is insufficient if the patient has not stopped menstruating for 12 months.

